5. CONSIDERATIONS FOR DATA ANALYSES AND DATA HANDLING CONVENTIONS

Table 2 provides an overview of the appendices within the RAP for outlining general considerations for data analyses and data handling conventions.

Table 2 Overview of Relevant Appendices

Section	Component
11.1	Appendix 1: Protocol Deviation Management and Definitions for Per Protocol Analysis
11.2	Appendix 2: Time & Events
11.3	Appendix 3: Assessment Windows
11.4	Appendix 4: Treatment States and Phases
11.5	Appendix 5: Data Display Standards & Handling Conventions
11.6	Appendix 6: Derived and Transformed Data
11.7	Appendix 7: Premature Withdrawals & Handling of Missing Data
11.8	Appendix 8: Values of Potential Clinical Importance
11.9	Appendix 9: Multicenter Studies
11.10	Appendix 10: Examination of Covariates and Subgroups
11.11	Appendix 11: Multiple Comparisons & Multiplicity
11.12	Appendix 12: Model Checking and Diagnostics for Statistical Analyses
11.13	Appendix 13: Medication Groupings

6. STUDY POPULATION ANALYSES

6.1. Overview of Planned Analyses

The study population analyses will be based on the ITT population unless otherwise specified.

[Table 3](#) provides an overview of the planned study population analyses, with full details of data displays being presented in Section [11.15](#).

Table 3 Overview of Planned Study Population Analyses

Display Type	Data Displays Generated		
	Table	Figure	Listing
Subject Disposition			
Study Populations [1]	Y		
Subjects Excluded from Populations [2]	Y (x2)		Y [3]
Reasons for Screen Failures [4]	Y		Y
Rescreened Subjects			Y
Subjects by Country and Site ID	Y		
Subjects by Region and Country	Y		
Subject Disposition	Y	Y	Y
Subject Disposition by Region and Country	Y		
Subject Survival Status	Y		
Subject Primary Endpoint Status	Y		
Study Treatment Discontinuation	Y	Y	Y
Study Treatment Discontinuation by Region and Country	Y		
Study Treatment Discontinuation Status by Study Completion Status	Y		
Subject Contact at Each Scheduled Visit	Y		
End of Study Contact	Y		
Subject Follow-up	Y	Y [5]	
Protocol Deviations			
Important Protocol Deviations	Y		Y
Events Leading to Exclusion of Data From Per-Protocol Analysis	Y		Y
Inclusion and Exclusion Criteria Deviations	Y		Y
Demography			
Demographics and Baseline Characteristics	Y (x2) [6]		Y [7]
Race and Racial Combinations	Y (x2) [6]		
Race and Racial Combinations Details	Y (x2) [6]		Y

Display Type	Data Displays Generated		
	Table	Figure	Listing
Subgroup Factors	Y (x2) [6]		
Medical Conditions (History)			
History of Prior glucagon-like peptide-1 (GLP-1) / dipeptidyl peptidase IV (DPP-IV) Use	Y		
Substance Use	Y		
Medical / Surgical Procedures	Y		
Medical Conditions	Y		
Medical Conditions: Coronary Artery Disease, Cerebrovascular Disease, or Peripheral Arterial Disease	Y		
Diabetic Eye Disease History	Y		
Nephropathy	Y		
Cancer History	Y		
Thyroid Cancer History	Y		
Family History of Cardiovascular Risk Factors	Y		
Medications			
Cardiovascular Medication Use Categories	Y (x2) [8]		Y
Anti-hyperglycaemic Medications	Y (x6) [9]		Y
Anti-hyperglycaemic Medication Categories	Y (x2) [10]		
Recorded Medications Other than Anti-hyperglycaemic [11]			Y
Relationship between ATC Level 1, Ingredient and Verbatim Text			Y
Exposure			
Study Treatment Exposure [12]	Y	Y (x2) [13]	Y
Planned and Actual Treatments			Y [14]
Dose Changes [12]	Y		
Treatment Compliance [12]	Y (x2) [15]		Y
Treatment Blind Broken			Y
Disclosure requirements			
EMA			
Subjects Enrolled by Country and Site ID [3]	Y		
Age Ranges [3]	Y		

NOTES :

- Y = Display Generated

[1] Include all populations.

[2] For all screened subjects and ITT population.

[3] Enrolled population.

[4] Include all screened subjects.

[5] CV and vital status.

[6] For the ITT population and the Safety population.

[7] Listing includes a subset of key assessments.

- [8] For the ITT population and the Safety population: each showing by visit, any post-baseline, and study end.
- [9] For the ITT population and the Safety population: baseline, any post-baseline, and study end.
- [10] For the ITT population and the Safety population, each showing categories of medications for baseline, any post-baseline, and study end.
- [11] See Section 6.2.3.
- [12] Safety population.
- [13] Duration of exposure including breaks, duration of exposure excluding breaks.
- [14] ITT population; format outputs to facilitate distribution to centers.
- [15] Treatment compliance including breaks, treatment compliance excluding breaks.

6.2. Supplementary Information for Study Population Tables and Listings

6.2.1. Disposition of Subjects

- Screened subjects who do not provide consent will be excluded from all summaries and listings.
- The Summary of Reasons for Screen Failures will exclude subjects who were rescreened, met eligibility criteria when rescreened and were randomized. For subjects who were rescreened and were not randomized, the summary will include the latest reason why the subject was not randomized.
- The Summary of Subject Contact at Each Scheduled Visit includes the number of subjects by visit type (in person with subject, telephone or video contact with subject, other contact with subject, contact with party other than subject, no contact).
- The Summary of End of Study Contacts includes the number and % of subjects by subject status during end of study window, type of end of study contact, and timing of end of study contact.
- There will be a Listing and a Summary of Inclusion and Exclusion Criteria Deviations for the ITT population.

6.2.2. Demographic and Baseline Characteristics

- The Summary of Demographics and Baseline Characteristics will be produced for both the ITT and Safety Populations and will include sex, age, age group (≤ 18 , $19-64$, ≥ 65 years), ethnicity (Hispanic or Latino, Not Hispanic or Latino), race detail, nephropathy, heart failure, duration of diabetes (years), height, weight, body mass index (BMI) (kg/m^2), BMI category (< 25 , ≥ 25 to < 30 , ≥ 30 to < 35 , ≥ 35), baseline HbA1c (Central or local lab, Central lab, local lab), baseline HbA1c category (Central or local lab, Central lab, local lab) ($\leq 6.5\%$, $> 6.5 - 7.0\%$, $> 7.0-8.0\%$, $> 8.0-9.0\%$, $> 9.0\%$), baseline eGFR (Central or local lab, Central lab, local lab), baseline eGFR category (Central or local lab, Central lab, local lab) (normal ≥ 90 , mild ≥ 60 to < 90 , moderate ≥ 30 to < 60 , and severe < 30 , and also < 60 and < 90), systolic blood pressure, and diastolic blood pressure. Summaries of eGFR will be based on

values computed using the protocol-specified formula based on the measured creatinine.

- Medical conditions will be summarized including cardiovascular disease risk categories (any, coronary artery disease, cerebrovascular disease, and peripheral arterial disease; also number of CV risk categories per subject).

6.2.3. Medications

- Details for all anti-hyperglycaemic medications and for all medications used within the 30 days prior to the onset and throughout the duration of an SAE, AE of special interest, or an AE leading to discontinuation of investigational product will be recorded in the eCRF. Medications used within the 30 days prior to the onset and throughout the duration of an SAE, AE of special interest, or an AE leading to discontinuation of investigational product will be included in listings but not summarized.
- Cardiovascular medications taken during the study will be recorded in the eCRF at each visit by class of agent. Use of cardiovascular medications by class of agent will be summarized for both the ITT and Safety Populations by visit, any post-baseline use, and use at latest visit, and will also be listed for the ITT population. It is possible that a cardiovascular medication may be recorded in more than one class of agent.
- Anti-hyperglycaemic medications will be summarized for both the ITT and the Safety Populations by Anatomical Therapeutic Chemical (ATC) level 1 (body system) and term for use at baseline, any post-baseline use, and use at latest visit, and will also be included in listings for the ITT population. In addition, a listing showing the relationship between ATC level 1, ingredient and verbatim text for these medications will be produced. Anti-hyperglycaemic medication use for both the ITT and Safety Populations at baseline, post-baseline, and latest visit will be summarized for the following categories of medications: none, insulin only, insulin alone or in combination with another anti-hyperglycaemic agent (AHA), insulin and 1 non-insulin AHA, insulin and 2 non-insulin AHAs, insulin and >2 non-insulin AHAs, no insulin and 1 non-insulin AHA, no insulin and 2 non-insulin AHAs, no insulin and >2 non-insulin AHAs, biguanide, sulfonylurea, non-sulfonylurea secretagogue, thiazolidinedione, alpha-glucosidase inhibitors, DPP-IV inhibitors, sodium-glucose co-transporter 2 (SGLT-2) inhibitor, GLP-1 analogues other than study drug, other anti-hyperglycaemic agent. These categories are shown in Section 11.13.

6.2.4. Exposure

- Extent of study treatment exposure will be summarized for the Safety population based on duration of exposure including breaks and duration of exposure excluding breaks, as continuous and categorical values for placebo and albiglutide (overall,

30mg, 50mg).

The frequency of subjects with dose escalations and with dose reductions will be summarized, along with the corresponding reasons. Number of dose escalations and dose reductions per subject will be summarized. Time to first dose escalation and time to first dose reduction will be summarized (continuous and categorical measure). In addition, the frequency of subjects by dose at latest dispensing (overall and by study treatment discontinuation status (yes, no)) will be summarized.

7. PRIMARY STATISTICAL ANALYSES

7.1. Primary Efficacy Analyses

7.1.1. Overview of Planned Primary Efficacy Analyses

The primary efficacy analyses will be based on the ITT population.

[Table 4](#) provides an overview of the planned primary efficacy analysis, and [Table 5](#) provides an overview of the planned sensitivity and supportive analyses of the primary endpoint; full details of data displays are presented in Section [11.15](#).

Table 4 Overview of Planned Primary Efficacy Analysis

Display Type	Absolute							
	Stats Analysis			Summary		Individual		
	T	F	L	T	F	F	L	
Primary Analysis of Primary Endpoint								
Time to MACE [1]	Y (x2) [2]	Y (x2) [3]	Y	Y (x2) [4]				

NOTES :

- T = Table, F = Figure, L = Listing, Y = Yes display generated.
- Stats Analysis = Represents TFL related to any formal statistical analyses (i.e. modelling) conducted.
- Summary = Represents TFL related to any summaries (i.e. descriptive statistics) of the observed raw data.
- Individual = Represents FL related to any displays of individual subject observed raw data.

[1] Time to first occurrence of adjudicated MACE (CV death, MI or stroke) during the CV Follow-up time period.

[2] Summary of results, raw SAS output.

[3] Kaplan-Meier and Cumulative Incidence plots.

[4] Incidence for all and components, incidence for first occurrence overall and by components.

Table 5 Overview of Planned Sensitivity and Supportive Analyses of the Primary Endpoint

Display Type	Absolute							
	Stats Analysis			Summary		Individual		
	T	F	L	T	F	F	L	
Key Sensitivity Analyses								
On-treatment Period [1]	Y	Y		Y				
On-therapy Period [2]	Y	Y		Y				
Per-Protocol Analysis	Y	Y		Y				
Other Sensitivity Analyses								
Excluding unknown cause of death	Y	Y		Y				
Including additional data from publicly available sources in subjects withdrawing consent	Y	Y		Y				
Tipping Point Analysis		Y						

Display Type	Absolute						
	Stats Analysis			Summary		Individual	
	T	F	L	T	F	F	L
Forest Plot of primary and sensitivity analyses		Y					
Supportive Analyses and Summaries							
Subgroups [3]	Y	Y					
Recurrent events analyses	Y			Y (x3) [4]			
Censoring and follow-up time				Y			
Events By Time Periods [5]				Y			

NOTES :

- T = Table, F = Figure, L = Listing, Y = Yes display generated.
- Stats Analysis = Represents TFL related to any formal statistical analyses (i.e. modelling) conducted.
- Summary = Represents TFL related to any summaries (i.e. descriptive statistics) of the observed raw data.
- Individual = Represents FL related to any displays of individual subject observed raw data.

[1] On-treatment = first dose of study treatment to last dose of study treatment

[2] On-therapy = first dose of study treatment to last dose of study treatment + 56 days

[3] Subgroups are specified in Section [11.10](#)

[4] Number of Adjudicated MACE, MI, Stroke events

[5] Events during and after defined follow-up periods

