1. REPORTING & ANALYSIS PLAN SYNOPSIS

Overview	Key Elements of the RAP
Purpose	
 This RAP describes the planned analyses and outputs required for the final CSR and study disclosure related reporting for study GLP116174.
Protocol	
 This RAP is based on protocol amendment 3 (Dated: 04-APR-2017) of study GLP116174 (GSK Document No. : 2014N193553_03) and the most recent version of the electronic Case Report Form (eCRF).
Primary Objective	
 To assess the effect of albiglutide with respect to MACE (major adverse cardiovascular events) when added to glycaemic standard of care versus standard of care alone
Primary Endpoint	
 Time to first occurrence of adjudicated MACE (cardiovascular death, myocardial infarction, or stroke) 
The primary analysis will be non-inferiority. If the pre-specified non-inferiority criterion is met then superiority testing will be performed.

Study Design	
 Randomized, double blind, parallel-group, placebo-controlled, multicenter study Approximately 9400 subjects with type 2 diabetes and a previous history of cardiovascular disease and who do not have optimal glycaemic control will be randomly allocated in a 1:1 ratio to receive either once weekly albiglutide or matching placebo subcutaneous injections. All subjects will receive standard of care which can be adjusted by their usual care provider(s) during the study according to clinical need. The study will continue until it is projected that at least 611 adjudicated MACE events will have occurred while requiring that the projected median duration of subject follow-up be at least 1.5 years. Assuming a true hazard ratio of 1.0, 611 events will be needed to have 90% power to rule out a non-inferiority margin of 1.3 for the hazard ratio with two-sided type I error of 0.05. Once it is projected that the target number of MACE events will have been collected and that the projected median duration of subject follow-up is at least 1.5 years, a 3 month window will be defined for conducting the final face to face visit.

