11.4. Appendix 4: Treatment States and Phases

11.4.1. Treatment States for MACE

Treatment State	Definition
Pre-treatment	Event Date < Study Treatment Start Date
On-treatment	If event date is on or after treatment start date & on or before treatment stop date. Study Treatment Start Date ≤ Event Date ≤ Study Treatment Stop Date
Post-treatment	If event date is after the treatment stop date Event Date > Study Treatment Stop Date
Pre-therapy	Event Date < Study Treatment Start Date
On-therapy (during treatment or up to 56 days post-treatment)	If event date is on or after treatment start date & within 56 days after treatment stop date. Study Treatment Start Date ≤ Event Date ≤ Study Treatment Stop Date+56 days
Post-therapy	If event date is after the treatment stop date+56 days. AE Start Date > Study Treatment Stop Date+56 days

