11.4.3. Treatment States for lab and vitals data

Treatment State	Definition
On-treatment	If assessment date is after treatment start date & on or before treatment stop date. Study Treatment Start Date < Assessment Date ≤ Study Treatment Stop Date

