
 • Last IP stop date if complete date (day, month and year) is available • If Last IP Stop date is completely missing and the subject has a non-missing treatment start date, then use the earliest of the following two items: 
 • date of death, • latest of the following four items: 
 ○ last visit date (exclude 5 week post-IP telephone call date), ○ last date of most recent IP injection from the Investigational Product injection site reaction eCRF, ○ last date of last study treatment dose from Liver pharmacokinetic (PK) eCRF, ○ earlier of (date of study completion/withdrawal, last IP start date (if not treatment start date) + 20 weeks). • If Last IP stop date is partial (i.e., either only year, or month and year are nonmissing) then impute as the latest date on or before the earliest of the following two items: 
 • date of death • latest of the following three items: 
 ○ last visit date (exclude 5 week post-IP telephone call date) ○ last date of most recent IP injection from the Investigational Product injection site reaction eCRF, ○ last date of last study treatment dose from Liver PK eCRF that is consistent with the nonmissing date components.
Study Day

 • Calculated as the number of days from randomization date: 
 • Ref Date = Missing → Study Day = Missing • Ref Date < Randomization Date → Study Day = Ref Date – Randomization Date • Ref Date ≥ Randomization Date → Study Day = Ref Date – (Randomization Date) + 1
Treatment Day

 • Calculated as the number of days from treatment start date: 
 • Treatment Start Date = Missing → Treatment Day = Missing • Ref Date < Treatment Start Date → Treatment Day = Ref Date – Treatment Start Date • Ref Date ≥ Treatment Start Date → Treatment Day = Ref Date – (Treatment Start Date) + 1
Last CV Assessment Date

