11.6.3. Safety

Time to Death endpoint

- Time to Death is defined as follows:
For subjects who died, time to death is the date of death - start date +1.
For subjects who did not die, time to death (censored) is the censoring date – start date + 1.
Occurrence and date of death will be determined based on data recorded in the CEC Death form; if adjudicated death date is missing then investigator-reported death date will be used.
Start date and censoring date will be assigned based on the evaluation time period of interest as subsequently specified.

Evaluation Time Period for Vital Status

Time Period for Follow-up of Vital Status

The start date of the time period for capturing vital status is the date of randomization. The end of this time period is defined as follows:

- For all subjects known to have died, use the date of death
- Otherwise, use the Last Study Contact Date.

Any endpoints that occurred before the start of this time period are considered to be prior to the time

Time to Death endpoint
period for vital status, and any endpoints that occurred after the end of this time period are considered to be post the time period for vital status.
Time Period for On-treatment Deaths
The start date of the time period for capturing On-treatment deaths is the treatment start date for subjects who received study treatment, and the date of randomization otherwise. The end of this time period is defined as follows: 
 For subjects who did not receive study treatment, use the date of randomization For all subjects known to have died, use the earliest of the following two dates: treatment stop date and date of death. Otherwise, use the earliest of the following two dates: treatment stop date and Last Study Contact Date. If the censoring date as defined above for On-treatment deaths is after the censoring date as defined for the time period for follow-up of vital status, then use the censoring date as defined for the time period for follow-up of vital status. Any events that occurred before the start of this time period are considered to be prior to the time period for On-treatment deaths, and any events that occurred after the end of this time period are considered to be post the time period for On-treatment deaths.
Time Period for On-therapy Deaths

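### The On-treatment period ends on the day of the last weekly injection, so in subjects still dosing the event itself often decides whether it is counted

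*SAP*

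**What the plan says.** The On-treatment analysis is listed first under "Key Sensitivity Analyses" in Table 5 (SAP Section 7.1.1), with the period defined as "On-treatment = first dose of study treatment to last dose of study treatment". Section 11.4.1 turns this into a dating rule for MACE: "Study Treatment Start Date ≤ Event Date ≤ Study Treatment Stop Date". Anything later is Post-treatment: "Event Date > Study Treatment Stop Date". Section 11.6.4 ends the On-treatment CV period no later than the treatment stop date.

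The same zero-lag rule applies to On-treatment mortality in Section 11.6.3: "For all subjects known to have died, use the earliest of the following two dates: treatment stop date and date of death". It also applies to laboratory and vital-sign data in Section 11.4.3: "Study Treatment Start Date < Assessment Date ≤ Study Treatment Stop Date".

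Treatment stop date is "Last IP stop date if complete date (day, month and year) is available" (Section 11.6.1). Subjects receive "either once weekly albiglutide or matching placebo subcutaneous injections" (Section 1).

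Table 5 lists two other key sensitivity analyses: On-therapy, which runs 56 days past the last dose, and Per-Protocol, which has the same 56-day tail.

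**The concern.** A subject dosing on schedule spends six days of every seven after one injection and before the next. An event on one of those days that ends dosing (a death, or a MACE after which the drug is not resumed) fixes the previous injection as the last. The subject is then censored at that injection and the event is classed Post-treatment. The same non-fatal event followed by one more injection lies before the stop date and is counted. The censoring date is thus partly set by the outcome being analysed, which is informative censoring by construction.

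The result gets a hazard ratio, a confidence interval, non-inferiority and superiority p-values (Table 2.08) and a row on the forest plot of sensitivity analyses (Section 7.1.2). A gap between that row and the On-therapy row could come from the cut-off and not from any effect of exposure. On-treatment mortality (Table 3.003) is the plainest case, because every death ends dosing.

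**Working it through.** **1. Is the stop date an injection day?** Two places in the SAP say so.
- Section 7.1.2 writes the On-therapy limit as last dose plus 56 days, and Section 11.4.1 writes it as stop date plus 56 days. The two dates are treated as one.
- In the exposure example of Section 11.6.2, an uninterrupted change of dose level starts 7 days after the previous stop date. If the stop date were the end of the dosing interval, the next start would be 1 day later.

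The expected pen count in Section 11.6.2 (duration divided by 7, rounded up) fits either reading and does not discriminate.

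**2. Share of treatment-ending events counted.** Let the last injection be day 0 and the event day be 0 to 6, each equally likely (assumption).
- As written, only day 0 counts: 1/7 = 14.3% kept and 6/7 = 85.7% censored.
- If a fraction m of doses is missed, the censored share is 1 − (1 − m)/7. This is 87.1% at m = 10% and 88.6% at m = 20%.
- With a lag of k days and full adherence, the kept share is (k + 1)/7, to a maximum of 1. This is 57% at +3 days and 100% at +6 or more.

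**3. Effect of the missing-date rule.** If the stop date is completely missing, the imputed date can reach the date of death (Section 11.6.1). Suppose a share q of deaths has a missing stop date and all are imputed to the death date. The share counted is q + (1 − q)/7, which reaches one half at q = 5/12, or about 42%. Below that, most deaths in dosing subjects are still excluded.

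**4. Scale for MACE.** First the plan's own figure. Events = 4(z₀.₉₇₅ + z₀.₉₀)²/(ln 1.3)² = 4(1.960 + 1.282)²/(0.2624)² ≈ 611, as in Section 1.

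The SAP does not give the share f of MACE in dosing subjects that is fatal or treatment-ending, so a range is shown. The share lost is f × 6/7. Power against 1.3 at a true hazard ratio of 1.0 is Φ(ln 1.3 × √D/2 − 1.96), with D the events left.

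| f (assumed) | share lost | events lost of 611 | power |
|---|---|---|---|
| 10% | 8.6% | 52 | 87% |
| 20% | 17.1% | 105 | 84% |
| 30% | 25.7% | 157 | 80% |
| 40% | 34.3% | 209 | 75% |
| 50% | 42.9% | 262 | 69% |

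The base of 611 is for scale only. It is the target for the primary analysis, and an On-treatment analysis would start with fewer events.

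**5. Possible shift in the hazard ratio (invented inputs).** Take hazard ratios of 1.6 for treatment-ending and 1.15 for other MACE, with f = 30%. All events give 0.3 × 1.6 + 0.7 × 1.15 = 1.285. On-treatment gives (0.3/7 × 1.6 + 0.7 × 1.15)/(0.3/7 + 0.7) = 1.18. With f = 20% the values are 1.24 and 1.17, and with f = 40% they are 1.33 and 1.19. Other inputs could move the ratio the other way.

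**6. Visit-based endpoints.** For Table 2.53, the final assessment is the latest On-treatment date with both HbA1c and weight (Section 11.6.4). A subject who finishes on drug keeps the final visit only if an injection is recorded on that day or later. Otherwise the assessment falls back to an earlier visit, and Table 2.66 lists weight only at baseline and every 8 months. The Month 8 and 16 MMRM tables lose a value only when a subject's very last injection fell 1 to 6 days before that visit, so the effect there is minor.

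**The case against.** **The paired analyses.** On-therapy and Per-Protocol keep every event in the six-day gap. The forest plot shows them beside the On-treatment row, and mortality also has vital-status and On-therapy versions. No decision rule uses the On-treatment result, and the zero-lag definition is stated consistently. This stands as a limit on the consequence. It does not repair a separately labelled key analysis with its own p-values.

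**The rule is the same in both arms.** It distorts the hazard ratio only if the treatment effect differs between event types, or if resumption of dosing differs by arm. This stands, so the direction and size of any bias are unknown.

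**Stronger readings that a reader might infer, and that the SAP does not support:**
- *Such events count only on an injection day.* Three rules make exceptions. A completely missing stop date can be imputed up to the death date (Section 11.6.1). CV events whose dates are too incomplete to place are classed On-treatment (Section 11.7.2.2). A fatal MI or stroke is kept when its index event lies inside the window (Section 11.6.4).
- *Most fatal MACE in the trial are lost.* The 6/7 applies only to subjects still dosing at the event. Events well after discontinuation are properly post-treatment.
- *Mild events are kept and severe ones dropped.* The dividing line is whether dosing resumed. A major MI or stroke followed by another injection is kept.
- *The primary conclusion is at risk.* The primary ITT analysis does not use this window.

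**Conclusion.** The point holds within limits. The zero-lag cut-off makes censoring depend on the event in the On-treatment analyses. In subjects still dosing with a complete stop date, about 6 in 7 deaths and treatment-ending MACE would be excluded. This rests on timing being uniform over the dosing week and on the recorded stop date being the last injection date, as the exposure example implies. The share of all MACE lost cannot be derived from the SAP; assumed shares of 10% to 50% treatment-ending give 9% to 43% of MACE in dosing subjects.

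The analyses materially affected are On-treatment MACE (Table 2.08 and its forest-plot row), On-treatment mortality (Table 3.003) and the On-treatment composite metabolic endpoint (Table 2.53). The incomplete-date rules add an inconsistency: two identical deaths can be classified differently because one record lacks a stop date. This should be corrected before unblinding, but it does not threaten the primary inference.

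**What to change.** End the On-treatment analysis periods (MACE, death, adverse events, laboratory and vital-sign data) at treatment stop date + 7 days, capped at death and at the end of the relevant follow-up period. Leave On-therapy at +56 days. Align the note to Table 5 and Sections 7.1.2, 11.4.1, 11.4.3, 11.6.3 and 11.6.4. Under full adherence +6 days already captures every event in the dosing week; +7 is one whole dosing interval and simpler to state. It is a choice and not the only defensible lag, since Section 11.6.2 treats gaps of up to 10 days as no break.

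The cost is a wording change and one derived date, with no new data. The downside is that a few days of off-drug time are counted for subjects who stopped for other reasons. The change is credible only if made before unblinding.

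At minimum, label the zero-lag version descriptive, name On-therapy as the key on-drug analysis, and state beside the forest plot that the zero-lag row tends to exclude events that end dosing.
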